#### **9.2.2.2. Exclusion Criteria**

Patients meeting any of the following criteria will not be included in Phase 2 of the study:

1. Are of unknown sex.
2. Have a missing month and year of birth.
3. Have received a COVID-19 vaccine in the 270 days prior to cohort entry date (as defined in Section 9.2.3).
4. Have received both the COMIRNATY 2023-2024 Formula and a COVID-19 vaccine other than the COMIRNATY 2023-2024 Formula on the cohort entry date (defined in Section 9.2.3).

In both phases of the study, when creating the analytic population for each specific safety outcome of interest, individuals will be excluded if they experienced that safety outcome during the portion of the baseline period designated as the clean period ([Section 9.2.4](#)).

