**Table 2. Clean periods and risk intervals for safety outcomes of interest**

Outcome	Clean Period*	Vaccine Risk Interval*	Care Setting**
Acute disseminated encephalomyelitis	Days -28 to -1	Days 0 to 21	IP
Anaphylaxis	Days -30 to -1	Days 0 to 1	IP, ED
Bell's palsy	Days -183 to 0	Days 1 to 42	IP, OP
Cerebral venous sinus thrombosis	Days -365 to 0	Days 1 to 28	IP, OP
Convulsions/seizures, non-febrile	Days -42 to -1	Days 0 to 21	IP, OP
Encephalomyelitis	Days -183 to 0	Days 1 to 42	IP
Glomerulonephritis	Days -365 to 0***	Days 1 to 42***	IP, OP
Guillain-Barré syndrome	Days -365 to 0	Days 1 to 42	IP-primary position only
Herpes zoster	Days -270 to 0	Days 1 to 30	IP, OP
Immune-mediated myositis	Days -365 to 0***	Days 1 to 28	IP, OP
Immune thrombocytopenia	Days -365 to 0	Days 1 to 42	IP, OP
Kawasaki disease	Days -365 to 0	Days 1 to 21	IP, OP
Multi inflammatory syndrome	Days -365 to 0	Days 1 to 42	IP, ED
Multiple sclerosis	Days -365 to 0	Days 1 to 42***	IP, OP
Myocardial infarction	Days -365 to 0	Days 1 to 28	IP
Myocarditis/pericarditis	Days -365 to 0	Days 1 to 21	IP, OP

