Lastly, a descriptive analysis of the matched cohorts will focus specifically on outcomes related to pregnancy (spontaneous abortion, stillbirth, preterm birth, major congenital malformations and small for gestational age). Recipients of the COMIRNATY 2023-2024 Formula and comparators who are pregnant at cohort entry will be identified, and the timing of their vaccination in relation to their last menstrual period (LMP) will be characterized. Baseline characteristics will be descriptively compared among the pregnant COMIRNATY 2023-2024 Formula recipients and comparators. Among COMIRNATY 2023-2024 Formula recipients who are pregnant at cohort entry, as well as among pregnant comparators, the incidence of pregnancy outcomes (spontaneous abortion, stillbirth, preterm birth) during follow-up will be described. For those individuals whose pregnancy results in a live birth, the prevalence of major congenital malformations and small for gestational age in their infants will be descriptively reported. Prevalence estimates will be reported separately for infants whose mothers received the COMIRNATY 2023-2024 Formula when pregnant and infants whose mothers do not have a recorded vaccination of COMIRNATY 2023-2024. Due to the relatively short length of follow-up, comparative analyses relating to pregnancy and infant outcomes will not be performed.

All results from Phase 2 analyses will be presented in the Final Report.

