### 17.3. Appendix III – Safety Outcomes of Interest

All codes are ICD-10 diagnosis codes; all outcomes will be defined based on the presence of a single code unless otherwise specified. In order to qualify as an outcome, the outcome-specific codes must be identified during emergency department visits, inpatient hospitalizations, or outpatient visits, as detailed in [Table 2](#). Outpatient visits are defined through physician evaluation and management codes ([Section 17.2.3](#)).

\* Outcome codes marked with an asterisk are based on COVID-19 vaccine studies conducted as part of the FDA’s CBER BEST system.

- Acute disseminated encephalomyelitis (ADEM)\*
  - G04.00 – Acute disseminated encephalitis and encephalomyelitis, unspecified
- Anaphylaxis\*
  - T80.52XA – Anaphylactic reaction due to vaccination, initial encounter
  - T78.2XXA – Anaphylactic shock, unspecified, initial encounter
- Bell's palsy\*
  - G51.0 – Bell’s palsy
  - G51.8 – Other disorders of facial nerve
  - G51.9 – Disorder of facial nerve, unspecified
- Cerebral venous sinus thrombosis (CVST)
  - I67.6 – Nonpyogenic thrombosis of intracranial venous system
  - I63.6 – Cerebral infarction due to cerebral venous thrombosis, nonpyogenic
- Convulsions/seizures (non-febrile)
  - G40.001 – Localization-related (focal) (partial) idiopathic epilepsy and epileptic syndromes with seizures of localized onset, not intractable, with status epilepticus
  - G40.009 – Localization-related (focal) (partial) idiopathic epilepsy and epileptic syndromes with seizures of localized onset, not intractable, without status epilepticus
  - G40.011 – Localization-related (focal) (partial) idiopathic epilepsy and epileptic syndromes with seizures of localized onset, intractable, with status epilepticus
  - G40.019 – Localization-related (focal) (partial) idiopathic epilepsy and epileptic syndromes with seizures of localized onset, intractable, without status epilepticus
  - G40.101 – Localization-related (focal) (partial) symptomatic epilepsy and epileptic syndromes with simple partial seizures, not intractable, with status epilepticus

090177e1a5be86fe\Approved\Approved On: 19-Mar-2026 15:57 (GMT)

- G40.109 – Localization-related (focal) (partial) symptomatic epilepsy and epileptic syndromes with simple partial seizures, not intractable, without status epilepticus

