- O03.85 – Other venous complications following complete or unspecified spontaneous abortion
- O03.86 – Cardiac arrest following complete or unspecified spontaneous abortion
- O03.87 – Sepsis following complete or unspecified spontaneous abortion
- O03.88 – Urinary tract infection following complete or unspecified spontaneous abortion
- O03.89 – Complete or unspecified spontaneous abortion with other complications
- O03.9 – Complete or unspecified spontaneous abortion without complication
- O31.1 – Continuing pregnancy after spontaneous abortion of one fetus or more
- O31.2 – Continuing pregnancy after intrauterine death of one fetus or more
- O36.4 – Maternal care for intrauterine death
- CPT 59800 – Treatment of spontaneous abortion, first trimester
- CPT 59801 – Treatment of spontaneous abortion, first trimester
- CPT 59810 – Treatment of spontaneous abortion, second trimester
- CPT 59811 – Treatment of spontaneous abortion, second trimester
- Stillbirth
  - O31.2 – Continuing pregnancy after intrauterine death of one fetus or more
  - O36.4 – Maternal care for intrauterine death
  - P95 – Stillbirth
  - Z37.1 – Single stillbirth
  - Z37.3 – Twins, one liveborn and one stillborn
  - Z37.4 – Twins, both stillborn

---

 CPT copyright 2024 American Medical Association. All rights reserved.

- Z37.60 – Multiple births, unspecified, some liveborn
- Z37.61 – Triplets, some liveborn
- Z37.62 – Quadruplets, some liveborn
- Z37.63 – Quintuplets, some liveborn
- Z37.64 – Sextuplets, some liveborn
- Z37.69 – Other multiple births, some liveborn
- Z37.7 – Other multiple births, all stillborn
- Preterm birth
  - O60.1 – Preterm labor with preterm delivery
  - P07.2 – Extreme immaturity of newborn
  - P07.3 – Preterm [premature] newborn [other]
  - P07.30 – Preterm newborn, unspecified weeks of gestation
  - P07.31 – Preterm newborn, gestational age 28 completed weeks
  - P07.32 – Preterm newborn, gestational age 29 completed weeks
  - P07.33 – Preterm newborn, gestational age 30 completed weeks
  - P07.34 – Preterm newborn, gestational age 31 completed weeks
  - P07.35 – Preterm newborn, gestational age 32 completed weeks
  - P07.36 – Preterm newborn, gestational age 33 completed weeks
  - P07.37 – Preterm newborn, gestational age 34 completed weeks
  - P07.38 – Preterm newborn, gestational age 35 completed weeks
  - P07.39 – Preterm newborn, gestational age 36 completed weeks
- Small for gestational age

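### Two continuing-pregnancy codes (O31.1, O31.2) count as spontaneous abortion, so losses before cohort entry and pregnancies that end in live birth can enter the descriptive incidence

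*Protocol*

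**What the plan says.** Section 17.3 (Appendix III) lists, under spontaneous abortion, "O31.1 – Continuing pregnancy after spontaneous abortion of one fetus or more" and "O31.2 – Continuing pregnancy after intrauterine death of one fetus or more". O31.2 appears again under stillbirth, as does O36.4. The general rule at the head of the appendix is that "all outcomes will be defined based on the presence of a single code unless otherwise specified". Nothing further is specified for spontaneous abortion.

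Section 9.7.2.4 defines the population: "Recipients of the COMIRNATY 2023-2024 Formula and comparators who are pregnant at cohort entry will be identified". Among these women, "the incidence of pregnancy outcomes (spontaneous abortion, stillbirth, preterm birth) during follow-up will be described". Infant outcomes are then reported on a live-birth denominator, introduced with "For those individuals whose pregnancy results in a live birth".

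Prevalent outcomes are handled in Section 9.2.2.2, where "individuals will be excluded if they experienced that safety outcome during the portion of the baseline period designated as the clean period". The outcome-specific windows are in Table 2, titled "Clean periods and risk intervals for safety outcomes of interest". Its 20 rows are the general safety outcomes; no pregnancy outcome has a row.

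**The concern.** Apart from the continuing-pregnancy codes, O36.4 and the procedure codes, the spontaneous-abortion list consists of missed abortion (O02.1) and the O03 series. O31.1 and O31.2 are different in kind: by their own labels the pregnancy goes on. Two consequences follow.

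First, timing. A woman whose singleton pregnancy was lost before cohort entry is not pregnant at entry and drops out of the population. A woman who lost one of several fetuses before entry is still pregnant and stays in it. If her code is recorded at a later visit, the loss is dated after vaccination, or after the comparator's qualifying encounter, although it came before.

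Second, classification. The same pregnancy can be reported as a spontaneous abortion, then as a preterm or other live birth, with its infant in the malformation and small-for-gestational-age denominators.

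At stake is the accuracy of a described incidence in a safety study that Section 7 calls a condition of authorization. A reader of the final report would take that figure as the share of pregnancies lost after vaccination.

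**Working it through.** The protocol states no sample size, event count or rate for spontaneous abortion, so there is no figure to reproduce. The check traces the definition through the protocol.

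1. **What triggers the outcome.** One listed code (Section 17.3). Where the authors want more than one code they say so: the multi inflammatory syndrome entry in the same appendix requires a COVID-19 code together with a second code. No such condition is attached to spontaneous abortion, and there is no rule that the pregnancy must have ended.
2. **Who is at risk.** Women pregnant at cohort entry (Section 9.7.2.4). A woman with an earlier co-fetus loss and a continuing pregnancy qualifies.
3. **When an event counts.** During follow-up, judged by when the code is recorded.
4. **What removes earlier events.** Only the clean period (Section 9.2.2.2), which takes its length from Table 2. With no row for pregnancy outcomes, there is no period to apply. Table 2 also sets the care settings, so no setting rule confines these codes to a hospital or delivery claim.
5. **What prevents double classification.** Nothing written. No order of precedence is given among spontaneous abortion, stillbirth and live birth, and the live-birth denominator does not exclude women already counted as a spontaneous abortion. O31.2 and O36.4 each sit in two lists, so a single code satisfies two outcomes.

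Steps 1 to 4 together allow a pre-entry co-fetus loss to be counted as a post-entry spontaneous abortion. Steps 1 and 5 allow one pregnancy to be counted as both lost and live-born.

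**Size, on assumed inputs only.** None of these inputs is in the protocol.

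Let m be the share of pregnancies at entry that are multiple, p the share of those with a continuing-pregnancy code in follow-up, and r the true risk of post-entry spontaneous abortion. The added share is m × p, and the relative overstatement is m × p / r.

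- Low: m = 1%, p = 5%, r = 15%. Added share 0.01 × 0.05 = 0.0005; 0.0005 / 0.15 = 0.3%.
- High: m = 4%, p = 30%, r = 5%. Added share 0.04 × 0.30 = 0.012; 0.012 / 0.05 = 24%.

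Assuming the coded share s directly (0.2% to 1%), with r from 3% to 10%, the overstatement is s / r:

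- 0.002 / 0.10 = 2%
- 0.005 / 0.05 = 10%
- 0.01 / 0.03 = 33%

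Both calculations treat every coded woman as a wrongly added event with no other qualifying code. Some would also carry O02.1 or an O03 code, so for given inputs these figures are upper values.

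**The case against.** **A fetus was lost.** O31.1 records a real event, and the protocol never says that a spontaneous abortion must end the pregnancy. The stillbirth list includes Z37.3 and Z37.60 to Z37.69, which cover multiple births with some infants born alive, so partial losses are counted there. This stands in part: the codes carry information and should not be discarded. It does not settle the matter. The analysis identifies pregnant women and then follows those whose pregnancy ends in live birth, which is reporting per woman or pregnancy. The Z37 codes record the outcome of delivery, whereas O31.1 describes a continuing state and does not date the loss.

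**The list cites a published validation study of claims algorithms for pregnancy outcomes.** That source may contain a hierarchy or link codes to a pregnancy episode. It cannot be checked here. The protocol transcribes none of that logic, so the single-code default governs.

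**This belongs in a separate analysis plan.** Section 7 describes the document as a combined protocol and statistical analysis plan, and Annex 1 lists no standalone documents. The code list is the operative definition.

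**The analysis is descriptive and conditional on sample size.** This stands. Section 9.7.2.4 rules out comparative analyses of pregnancy and infant outcomes. A reader might infer that differing rates of multiple gestation would bias a vaccine-versus-comparator miscarriage estimate. No such estimate is planned, so the protocol does not support that reading. Someone could still set the two described incidences side by side.

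**Pre-entry losses are inferred.** Also fair. The text allows them to be counted. Whether any are depends on the code being recorded again after entry, which the protocol cannot show.

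**Conclusion.** The point holds in limited form. As written, the definition can misdate a co-fetus loss that preceded cohort entry and can classify one pregnancy as both spontaneously aborted and live-born. The error is upward in both cohorts and affects only a described incidence; no planned rate ratio or test depends on it.

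The size is unknown and possibly small. The range of roughly 0.3% to 33% comes wholly from assumed inputs. Its top pairs the highest assumed code share with the lowest assumed risk, so a reader should not take it as an estimate. Nor does the protocol support a statement that the reported incidence will contain pre-vaccination events, only that nothing in it keeps them out.

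The conclusion rests on the literal single-code rule, on the absence of a Table 2 row for pregnancy outcomes, and on reading Section 9.7.2.4 as reporting per woman or pregnancy.

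**What to change.** - Take O31.1 and O31.2 out of the pregnancy-level spontaneous-abortion count. Report them on a separate line as partial loss in multiple gestation, counted only when the first such code falls after cohort entry and none lies between last menstrual period and entry.
- If O31.2 stays under stillbirth, apply the same first-code-after-entry rule there, and label its place on the partial-loss line as a breakdown so that it is not a second count.
- Assign O31.2 and O36.4 each to one outcome, so that a single code no longer satisfies both spontaneous abortion and stillbirth. O36.4 is not labelled as a continuing-pregnancy code and should not disappear as a side effect of this edit; state explicitly where it goes.
- State in Section 9.7.2.4 that the unit of analysis is the pregnancy.

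The cost is an edit to the code lists and a short dating rule. A few complete losses coded only to O31.1 or O31.2 would leave the main count, which becomes slightly lower; the separate line keeps those first coded after entry visible. The revised list may depart from the cited published algorithm, and the protocol should note this.

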## 17.4. Appendix IV – Covariate Codes

### 17.4.1. Comorbidities

#### 17.4.1.1. Asthma

##### 17.4.1.1.1. ICD-10-CM Codes

J45.20	Mild intermittent asthma, uncomplicated
J45.21	Mild intermittent asthma with (acute) exacerbation
J45.22	Mild intermittent asthma with status asthmaticus
J45.30	Mild persistent asthma, uncomplicated
J45.31	Mild persistent asthma with (acute) exacerbation
J45.32	Mild persistent asthma with status asthmaticus
J45.40	Moderate persistent asthma, uncomplicated
J45.41	Moderate persistent asthma with (acute) exacerbation
J45.42	Moderate persistent asthma with status asthmaticus
J45.50	Severe persistent asthma, uncomplicated
J45.51	Severe persistent asthma with (acute) exacerbation
J45.52	Severe persistent asthma with status asthmaticus
J45.901	Unspecified asthma with (acute) exacerbation
J45.902	Unspecified asthma with status asthmaticus
J45.909	Unspecified asthma, uncomplicated
J45.991	Cough variant asthma
J45.998	Other asthma
J82.83	Eosinophilic asthma

### 17.4.1.2. Non-Malignant Blood Disorders

#### 17.4.1.2.1. ICD-10-CM Codes

D55.0	Anemia due to G6PD deficiency
D55.1	Anemia due to other disorders of glutathione metabolism
D55.21	Anemia due to pyruvate kinase deficiency
D55.29	Anemia due to other disorders of glycolytic enzymes
D55.3	Anemia due to disorders of nucleotide metabolism
D55.8	Other anemias due to enzyme disorders
D55.9	Anemia due to enzyme disorder, unspecified
D56.0	Alpha thalassemia
D56.1	Beta thalassemia
D56.2	Delta-beta thalassemia
D56.3	Thalassemia minor
D56.4	Hereditary persistence of fetal hemoglobin [HPFH]
D56.5	Hemoglobin E-beta thalassemia
D56.8	Other thalassemias
D56.9	Thalassemia, unspecified
D57.00	Hb-SS disease w/ crisis, unspecified
D57.01	Hb-SS disease w/ acute chest syndrome
D57.02	Hb-SS disease w/ splenic sequestration
D57.03	Hb-SS disease with cerebral vascular involvement
D57.04	Hb-SS disease with dactylitis
D57.09	Hb-SS disease with crisis with other specified complication
D57.1	Sickle cell disease w/o crisis
D57.20	Sickle cell/Hb-C disease w/o crisis

D57.21	Sickle cell/Hb-C disease w/ crisis
D57.211	Sickle cell/Hb-C disease w/ acute chest syndrome
D57.212	Sickle cell/Hb-C disease w/ splenic sequestration
D57.213	Sickle-cell/Hb-C disease with cerebral vascular involvement
D57.214	Sickle-cell/Hb-C disease with dactylitis
D57.218	Sickle-cell/Hb-C disease with crisis with other specified complication
D57.219	Sickle cell/Hb-C disease w/ crisis, unspecified
D57.3	Sickle cell trait
D57.40	Sickle cell thalassemia w/o crisis
D57.41	Sickle-cell thalassemia w/ crisis
D57.411	Sickle cell thalassemia w/ acute chest syndrome
D57.412	Sickle cell thalassemia w/ splenic sequestration
D57.413	Sickle-cell thalassemia, unspecified, with cerebral vascular involvement
D57.414	Sickle-cell thalassemia, unspecified, with dactylitis
D57.418	Sickle-cell thalassemia, unspecified, with crisis with other specified complication
D57.419	Sickle cell thalassemia w/ crisis, unspecified
D57.42	Sickle-cell thalassemia beta zero without crisis
D57.431	Sickle-cell thalassemia beta zero with acute chest syndrome
D57.432	Sickle-cell thalassemia beta zero with splenic sequestration
D57.433	Sickle-cell thalassemia beta zero with cerebral vascular involvement
D57.434	Sickle-cell thalassemia beta zero with dactylitis
D57.438	Sickle-cell thalassemia beta zero with crisis with other specified complication

D57.439	Sickle-cell thalassemia beta zero with crisis, unspecified
D57.44	Sickle-cell thalassemia beta plus without crisis
D57.451	Sickle-cell thalassemia beta plus with acute chest syndrome
D57.452	Sickle-cell thalassemia beta plus with splenic sequestration
D57.454	Sickle-cell thalassemia beta plus with dactylitis
D57.458	Sickle-cell thalassemia beta plus with crisis with other specified complication
D57.459	Sickle-cell thalassemia beta plus with crisis, unspecified
D57.80	Other sickle cell disorders w/o crisis
D57.811	Other sickle cell disorders w/ acute chest syndrome
D57.812	Other sickle cell disorders w/ splenic sequestration
D57.813	Other sickle-cell disorders with cerebral vascular involvement
D57.814	Other sickle-cell disorders with dactylitis
D57.818	Other sickle-cell disorders with crisis with other specified complication
D57.819	Other sickle cell disorders w/ crisis, unspecified
D58.0	Hereditary spherocytosis
D58.1	Hereditary elliptocytosis
D58.2	Other hemoglobinopathies
D58.8	Other specified hereditary hemolytic anemias
D58.9	Hereditary hemolytic anemia, unspecified
D59.0	Drug-induced autoimmune hemolytic anemia
D59.10	Autoimmune hemolytic anemia, unspecified
D59.11	Warm autoimmune hemolytic anemia
D59.12	Cold autoimmune hemolytic anemia

090177e1a5be86fe\Approved\Approved On: 19-Mar-2026 15:57 (GMT)

D59.13	Mixed type autoimmune hemolytic anemia
D59.19	Other autoimmune hemolytic anemia
D59.2	Drug-induced nonautoimmune hemolytic anemia
D59.30	Hemolytic-uremic syndrome, unspecified
D59.31	Infection-associated hemolytic-uremic syndrome
D59.32	Hereditary hemolytic-uremic syndrome
D59.39	Other hemolytic-uremic syndrome
D59.4	Other nonautoimmune hemolytic anemias
D59.5	Paroxysmal nocturnal hemoglobinuria [Marchiafava-Micheli]
D59.6	Hemoglobinuria due to hemolysis from other external causes
D59.8	Other acquired hemolytic anemias
D59.9	Acquired hemolytic anemia, unspecified
D60.0	Chronic acquired pure red cell aplasia
D60.1	Transient acquired pure red cell aplasia
D60.8	Other acquired pure red cell aplasias
D60.9	Acquired pure red cell aplasia, unspecified
D61.01	Constitutional (pure) red blood cell aplasia
D61.02	Shwachman-Diamond syndrome
D61.09	Other constitutional aplastic anemia
D61.1	Drug-induced aplastic anemia
D61.2	Aplastic anemia due to other external agents
D61.3	Idiopathic aplastic anemia
D61.810	Antineoplastic chemotherapy induced pancytopenia
D61.811	Other drug-induced pancytopenia

090177e1a5be86fe\Approved\Approved On: 19-Mar-2026 15:57 (GMT)

D61.818	Other pancytopenia
D61.82	Myelophthisis
D61.89	Other specified aplastic anemias and other bone marrow failure syndromes
D61.9	Aplastic anemia, unspecified
D62	Acute posthemorrhagic anemia
D63.0	Anemia in neoplastic disease
D63.1	Anemia in chronic kidney disease
D63.8	Anemia in other chronic diseases classified elsewhere
D64.0	Hereditary sideroblastic anemia
D64.1	Secondary sideroblastic anemia due to disease
D64.2	Secondary sideroblastic anemia due to drugs and toxins
D64.3	Other sideroblastic anemias
D64.4	Congenital dyserythropoietic anemia
D64.81	Anemia due to antineoplastic chemotherapy
D64.89	Other specified anemias
D64.9	Anemia, unspecified
D65	Disseminated intravascular coagulation
D66	Hereditary factor VIII deficiency
D67	Hereditary factor IX deficiency
D68.00	Von Willebrand disease, unspecified
D68.1	Hereditary factor XI deficiency
D68.01	Von Willebrand disease, type 1
D68.020	Von Willebrand disease, type 2A
D68.021	Von Willebrand disease, type 2B

D68.022	Von Willebrand disease, type 2M
D68.023	Von Willebrand disease, type 2N
D68.029	Von Willebrand disease, type 2, unspecified
D68.03	Von Willebrand disease, type 3
D68.04	Acquired von Willebrand disease
D68.09	Other von Willebrand disease
D68.1	Hereditary factor XI deficiency
D68.2	Hereditary deficiency of other clotting factors
D68.311	Acquired hemophilia
D68.312	Antiphospholipid antibody with hemorrhagic disorder
D68.318	Other hemorrhagic disorder due to intrinsic circulating anticoagulants, antibodies, or inhibitors
D68.32	Hemorrhagic disorder due to extrinsic circulating anticoagulants
D68.4	Acquired coagulation factor deficiency
D68.51	Activated protein C resistance
D68.52	Prothrombin gene mutation
D68.59	Other primary thrombophilia
D68.61	Antiphospholipid syndrome
D68.62	Lupus anticoagulant syndrome
D68.69	Other thrombophilia
D68.8	Other specified coagulation defects
D68.9	Coagulation defect, unspecified
D69.0	Allergic purpura
D69.1	Qualitative platelet defects

D69.2	Other nonthrombocytopenic purpura
D69.3	Immune thrombocytopenic purpura
D69.41	Evans syndrome
D69.42	Congenital and hereditary thrombocytopenia purpura
D69.49	Other primary thrombocytopenia
D69.51	Post-transfusion purpura
D69.59	Other secondary thrombocytopenia
D69.6	Thrombocytopenia, unspecified
D69.8	Other specified hemorrhagic conditions
D69.9	Hemorrhagic condition, unspecified
D70.0	Congenital agranulocytosis
D70.1	Agranulocytosis secondary to cancer chemotherapy
D70.2	Other drug-induced agranulocytosis
D70.3	Neutropenia due to infection
D70.4	Cyclic neutropenia
D70.8	Other neutropenia
D70.9	Neutropenia, unspecified,
D71	Functional disorders of polymorphonuclear neutrophils
D72.0	Genetic anomalies of leukocytes
D72.10	Eosinophilia, unspecified
D72.110	Idiopathic hypereosinophilic syndrome [IHES]
D72.111	Lymphocytic Variant Hypereosinophilic Syndrome [LHES]
D72.118	Other hypereosinophilic syndrome
D72.119	Hypereosinophilic syndrome [HES], unspecified

090177e1a5be86fe\Approved\Approved On: 19-Mar-2026 15:57 (GMT)

D72.12	Drug rash with eosinophilia and systemic symptoms syndrome
D72.18	Eosinophilia in diseases classified elsewhere
D72.19	Other eosinophilia
D72.810	Lymphocytopenia
D72.818	Other decreased white blood cell count
D72.819	Decreased white blood cell count, unspecified
D72.820	Lymphocytosis (symptomatic)
D72.821	Monocytosis (symptomatic)
D72.822	Plasmacytosis
D72.823	Leukemoid reaction
D72.824	Basophilia
D72.825	Bandemia
D72.828	Other elevated white blood cell count
D72.829	Elevated white blood cell count, unspecified
D72.89	Other specified disorders of white blood cells
D72.9	Disorder of white blood cells, unspecified

